Engage in Them. Despite their widespread availability and affordability, very few patients with prediabetes participate in a DPP or use metformin. In the first four years of the NDPP, just 35,844 of the estimated 84 million US adults with prediabetes participated in one of the 435 CDC-recognized DPPs. Among individuals who participated in these DPPs, only 43% completed the 16 core sessions (compared to 95% in the original DPP trial), resulting in 4.2% mean weight loss among participants after one year (compared to 7.2% in the original DPP trial). Fewer than 1% of US adults with prediabetes are using metformin, despite its availability, safety, and low cost. At our own institution, the University of Michigan (U-M), Premier Care, the health insurance plan chosen by nearly three in four U-M employees who take up U-M insurance, covers DPPs at no cost to plan members with prediabetes and offers metformin as a Tier one (i.e., lowest co-pay) medication. Despite little to no cost-sharing for these evidence-based strategies to prevent T2DM, in the last year just 8% of U-M employees with prediabetes and Premier Care participated in a DPP, and only 8% took metformin. These major gaps illustrate the critical need for effective, scalable, and sustainable approaches to increase engagement of patients with prediabetes in evidence-based strategies to prevent or delay their progression to T2DM.

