Measures taken to protect privacy and confidentiality are described in the *Privacy and Confidentiality Measures* section of this protocol.

Strategies to Maximize Retention and Data Collection. Participants will receive \$50 when they complete each assessment consisting of the online survey, weigh-in, and A1c test. They will also receive email, text messages, and phone calls to remind them to complete these tasks. We used this approach to limit attrition rates to 2% at 12 weeks in our pilot study and to less than 10% at nine months in two previous trials.^{39,41}

Statistical Design

Sample Size

Based on data from previous studies, in the Enhanced Control Arm we anticipate a mean 12-month absolute HbA1c change (defined as the 12-month measure minus the baseline measure) of 0.0%, a mean 12-month absolute HbA1c decrease of 0.2% in both the Financial Incentives Arm and the Tailored Messages Arm, and a mean 12-month absolute HbA1c decrease of 0.4%

in the Combo Arm. Assuming a 0.4% standard deviation for 12-month HbA1c change in each arm and using an α of 0.017 to adjust for three main comparisons, 85 subjects per arm will provide 99% power to detect the difference between the Financial Incentives Plus Tailored Messages and Enhanced Control Arms (H1a), and 80% power to detect differences between the Combo Arm and the Tailored Messages Arm and the Financial Incentives Arm (H1b). With this sample size, we will also be able to detect meaningful differences (Cohen's d of 0.5 or larger) in secondary outcomes of weight, months of engagement in a Diabetes Prevention Program (DPP), months of taking metformin, and months of engagement in a DPP or taking metformin. To account for possible attrition we have conservatively inflated our sample size by 10% and will enroll 380 participants.

Analysis Plans

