Our primary analytic approach will use ordinary least squares (OLS) regression models for continuous outcomes, adjusting for two stratification variables used in randomization (household income and autonomous motivation to prevent diabetes). To assess balance in randomization, we will compare baseline survey measures across arms. Additionally, we expect some missing data on baseline measures and outcomes and will assess the extent and pattern of missingness (e.g., monotone missingness) and predictors of missing outcomes. If we find a baseline measure to be predictive of missing outcome data, we will also adjust for this measure in analyses of outcomes. As an alternative analytic strategy, we will also use mixed-effects models. We will assess for consistency in the results between the two analytic approaches. If more than 10% of the 12-month data are missing, we will also use a multiple imputation strategy in which we will generate ten imputed datasets for missing data using a sequential regression multivariable imputation method, including intervention arms and other baseline variables.¹⁸⁵ The estimates from both the OLS and mixed-effects model analyses using imputed datasets will then be combined using the method of Rubin and Little.¹⁸⁶ All analyses of outcomes will use an intent-to-treat approach and a Bonferroni corrected α of 0.017. Data will be analyzed by a Data Analyst who will be blinded to arm assignment until all primary outcome data have been collected.

Aim 1: Compare the effectiveness of financial incentives plus tailored messages based on SDT principles, financial incentives, and tailored messages based on SDT principles in decreasing hemoglobin A1c, and weight, and in increasing participation in a DPP or use of metformin.

H1a: The mean decrease in HbA1c will be greater in the Combo Arm than in the Enhanced Control Arm.

H1b: The mean decrease in HbA1c will be greater in the Combo Arm than in the Financial Incentives Arm and the Tailored Messages Arm.

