Mean 12-month change in HbA1c (defined as the 12-month measure minus the baseline measure) will be reported by arm. To test H1a and H1b, we will use an OLS regression model with 12-month change in HbA1c as the response variable. This model will include an indicator for each of the three arms (with the Financial Incentives Plus Tailored Messages Arm as the reference), stratification factors, baseline HbA1c values, and any baseline measures that are predictive of missing 12-month data. We will use similar, separate OLS regression models to predict our secondary outcomes of 12-month changes in weight (defined as the difference between the 12-month and baseline measures) and mean number of months (calculated out of 12 months to account for those who drop out before 12 months) in which individuals were engaged in a DPP, mean months in which individuals had a metformin PDC of at least 0.8, and mean months in which individuals were engaged in a DPP or had a metformin PDC of at least 0.8.

In alternate analyses, we will fit separate mixed-effects models for the primary and secondary outcomes using baseline, 6, and 12-month data as response variables and with time, study arm indicators, and interactions between time and study arm indicators as predictors and participants as random intercepts. We expect the changes in outcomes in intervention arms to be gradual over time and anticipate these longitudinal data models will confirm findings from our primary analytic approach to testing H1a and H1b, but if the findings differ, we will examine the source of any differences. For models for months of engagement in a DPP or use of metformin, we will first assess the distribution for skewness and, if more appropriate, a count data model (e.g., zero-inflated negative binomial) will be used instead of OLS.

Aim 2: Identify mediators and moderators of the effectiveness of financial incentives plus tailored messages based on SDT principles, financial incentives, and tailored messages based on SDT principles.

H2a: Combo Arm on 12-month change in HbA1c will be mediated by changes in autonomous motivation and changes in controlled motivation.

H2b: Effects of the Financial Incentives Arm on 12-month change in HbA1c will be mediated by changes in controlled motivation.

H2c: Effects of the Tailored Messages Arm on 12-month change in HbA1c will be mediated by changes in autonomous motivation.

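### The OLS outcome models name no robust variance, so a Combo contrast gets a wrong standard error when its two arms' average variance differs from the four-arm average; Combo versus Financial Incentives on engaged months is the most exposed

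*Combined protocol and SAP*

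**What the plan says.** Under Analysis Plans, Aim 1, the primary test is a single four-arm model: "To test H1a and H1b, we will use an OLS regression model with 12-month change in HbA1c as the response variable". It has three arm indicators with the Combo Arm as reference, the stratification factors and baseline HbA1c. The secondary outcomes follow the same form: "We will use similar, separate OLS regression models to predict our secondary outcomes of 12-month changes in weight", followed by mean months of DPP engagement, of metformin coverage, and of either.

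Sample Size assumes one spread for all arms: "Assuming a 0.4% standard deviation for 12-month HbA1c change in each arm". The error rate is set there by "using an α of 0.017 to adjust for three main comparisons", and Analysis Plans repeats it: "All analyses of outcomes will use an intent-to-treat approach and a Bonferroni corrected α of 0.017".

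Neither section names a robust, heteroscedasticity-consistent or arm-specific variance. The alternate mixed models add a participant random intercept but no variance that differs by arm. For engaged months only, the plan will look at skewness and may use a count model, such as a zero-inflated negative binomial, in place of OLS. Aim 4 uses OLS again, comparing the Enhanced Usual Care arm with external controls, and also names no variance method.

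**The concern.** With conventional OLS standard errors, every pairwise contrast uses one residual variance estimated from all four arms. Equal allocation does not protect a pairwise test here, because the two arms outside the contrast also feed that variance.

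Engaged months are where this is most plausible. The outcome is a bounded count, and Background Information reports low uptake before the trial: "just 8% of U-M employees with prediabetes and Premier Care participated in a DPP, and only 8% took metformin". At low uptake the spread of such a count rises with its mean. Two arms are paid to engage and two are not. If payment works, Combo and Financial Incentives have the larger spread, and their comparison borrows a variance that is too small from the other two arms. That comparison is the plan's own test of adding tailored messages to incentives. At stake are its false-positive rate and interval coverage. None of this depends on correlation within the five-person incentive groups; it arises with fully independent participants.

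**Working it through.** **Inputs from the documents.** Target 85 per arm, equal allocation, SD 0.4 in each arm, α 0.017. The assumed effects are "a mean 12-month absolute HbA1c decrease of 0.2% in both the Financial Incentives Arm and the Tailored Messages Arm" and, for Combo, "a mean 12-month absolute HbA1c decrease of 0.4" percentage points, with no change in Enhanced Control. Sidedness is not stated; two-sided testing (z = 2.387) reproduces the stated power.

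**The plan's own figure.** SE = 0.4 × √(2/85) = 0.0614. For a difference of 0.2: 0.2/0.0614 = 3.26, and Φ(3.26 − 2.387) = 0.81, against 80% stated. For 0.4 the power exceeds 0.99, against 99% stated. The sample size is sound under its equal-SD assumption.

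**Formula for unequal spread.** With equal arm sizes, the ratio of pooled to true SE for a contrast is

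r = √(mean of the four arm variances / mean of the two compared variances),

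and the true error is 2 × (1 − Φ(2.387 × r)). If the two means are equal, r = 1 and the nominal level holds. If r exceeds 1 the test is conservative.

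**Engaged months.** Assume a share p ever engages, with months uniform on 1 to 11 among those who do (mean 6, mean square 46). The variance is then 46p − 36p². The documents give no uptake by arm, so the shares below are assumptions (C = Combo, F = Financial Incentives, T = Tailored Messages, E = Enhanced Control).

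| Shares C/F/T/E | Variances | Four-arm mean | r, C vs F | Error, C vs F | Error, C vs E |
|---|---|---|---|---|---|
| 0.40/0.40/0.35/0.30 | 12.64, 12.64, 11.69, 10.56 | 11.88 | 0.970 | 2.1% | 1.6% |
| 0.50/0.50/0.40/0.30 | 14.00, 14.00, 12.64, 10.56 | 12.80 | 0.956 | 2.2% | 1.5% |
| 0.25/0.25/0.16/0.16 | 9.25, 9.25, 6.44, 6.44 | 7.84 | 0.921 | 2.8% | 1.7% |
| 0.50/0.50/0.25/0.16 | 14.00, 14.00, 9.25, 6.44 | 10.92 | 0.883 | 3.5% | 1.4% |
| 0.50/0.50/0.16/0.16 | 14.00, 14.00, 6.44, 6.44 | 10.22 | 0.854 | 4.1% | 1.7% |
| 0.50/0.50/0.16/0.08 | 14.00, 14.00, 6.44, 3.45 | 9.47 | 0.822 | 5.0% | 1.3% |

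In the fifth row, for example, r = √(10.22/14.00) = 0.854 and 2.387 × 0.854 = 2.04, which gives 4.1%. For Combo versus Enhanced Control the pair mean is (14.00 + 6.44)/2 = 10.22, equal to the four-arm mean, so the level is kept.

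The upper figure is not a bound: shares of 0.30/0.30/0.08/0.08 give 5.2% by formula and 5.4% in simulation. With 0.16 in every arm the simulated error is 1.4% to 1.8%.

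Simulation of the last three rows with stratum covariates (6,000 trials each) gave 3.7%, 4.2% and 4.7% for the planned OLS test and 1.6% to 1.7% with HC3. Separate simulations without covariates (20,000 trials each) gave 1.4% to 1.9% for an unequal-variance standard error.

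**HbA1c.** SDs other than 0.4 are assumptions.
- Combo 0.5, others 0.4: four-arm mean (0.25 + 3 × 0.16)/4 = 0.1825; pair mean (0.25 + 0.16)/2 = 0.205; r = 0.944; error 2.4%.
- Combo 0.3, others 0.4: 0.1425 and 0.125; r = 1.068; error 1.1%, conservative.

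**Aim 4.** Assume 85 patients in the trial arm and 1,000 external controls, with SDs given in that order.
- SDs 0.5 and 0.4: pooled variance (84 × 0.25 + 999 × 0.16)/1083 = 0.167; pooled SE √(0.167 × (1/85 + 1/1000)) = 0.0462; true SE √(0.25/85 + 0.16/1000) = 0.0557; ratio 0.829. A 5% test runs at about 10%.
- SDs 0.3 and 0.4: pooled SE 0.0444, true SE 0.0349, ratio 1.27. A 5% test runs at about 1.3%.

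**The case against.** The strongest reply concerns engaged months: the plan provides for a count model instead of OLS. In the last three rows of the table, 65% to 69% of participants have zero months, which is the zero-heavy case that provision describes. This stands in part. The OLS error rates apply only if OLS is kept. But the switch is discretionary, is prompted by skewness rather than unequal spread, and does not reach HbA1c, weight or Aim 4.

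A reader might also infer more than the documents support:
- **That error bars are wrong whenever arms differ in spread.** They are not. What matters is the pair average against the four-arm average, and Combo versus Enhanced Control is nearly unaffected in the table.
- **That engaged months must differ in spread by construction.** They do so only if the arms engage differently. If all arms engage alike, the level is kept.
- **That the false-positive rate is two to three times nominal.** Only the more extreme assumed shares give that. The 8% figures describe insured employees generally, not consenting volunteers. Enhanced Control itself receives education, coverage reminders and feedback, and Tailored Messages adds enrolment support. Milder shares give 2.1% to 2.8%.
- **That the primary HbA1c tests are inflated.** No arm-specific SD is given. Hypothesis H2d expects effects to vary with income and future orientation, so unequal spread is plausible, but its size and direction are unknown. A larger spread from a larger Combo effect also sits poorly with Specific Aims, Aim 4, which reports that the Enhanced Usual Care arm improved most.

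**Conclusion.** The point holds as a specification gap of modest priority. As written, the plan lets the arms outside a contrast set its standard error. The worst exposure is one contrast, Combo versus Financial Incentives, on secondary outcomes: about 2.1% to 5.0% against 1.7%, conditional on incentives raising engagement, on OLS being kept, and on the assumed uptake model. For HbA1c and weight the effect is conditional and may run either way (1.1% or 2.4% in the two HbA1c cases tried). For Aim 4 the direction depends on which group has the larger spread, and the figures rest on assumed group sizes and SDs. The estimated differences themselves, and the stated sample size under its own assumptions, are unaffected.

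**What to change.** Add one sentence to Analysis Plans: all OLS outcome models in Aims 1 and 4 (HbA1c, weight, engaged months) report HC3 standard errors, or standard errors from arm-specific residual variances, and any count model uses robust standard errors.

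Specific Aims, Aim 4, says that the primary and secondary outcomes have already been analysed. For Aim 1 the robust results should therefore be reported as a disclosed re-analysis beside the conventional ones.

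The cost is a software option and somewhat wider intervals for some contrasts. In the 0.50/0.50/0.16/0.16 case the Combo versus Financial Incentives interval would be about 1/0.854 = 1.17 times as wide. Where arms have equal spread, almost nothing is lost.

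### The alternate mixed model omits the baseline HbA1c and strata adjustment of the primary OLS model, so the planned consistency check can pick up chance baseline imbalance as well as longitudinal modelling

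*Combined protocol and SAP*

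**What the plan says.** Under Analysis Plans, Aim 1, the primary OLS model for 12-month change in HbA1c contains arm indicators plus "stratification factors, baseline HbA1c values, and any baseline measures that are predictive of missing 12-month data". The next paragraph describes the alternate mixed model. Its responses are the baseline, 6- and 12-month values, and it is fitted "with time, study arm indicators, and interactions between time and study arm indicators as predictors", with a random intercept per participant. No baseline covariate, stratification factor or common baseline mean across arms is listed.

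The opening paragraph of Analysis Plans gives the comparison a purpose: "We will assess for consistency in the results between the two analytic approaches". Aim 1 adds that the longitudinal models are expected to confirm the OLS findings, and that the source of any difference will be examined. The opening paragraph also has a general rule that baseline predictors of missing outcomes will be adjusted for in outcome analyses.

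**The concern.** A consistency check is most informative when the two analyses differ in one respect. Here they differ in two: the longitudinal structure, and the covariate set. If the results diverge, the comparison alone cannot say which of the two is responsible.

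Baseline HbA1c is not a stratification factor, so arm means at baseline will differ by chance. OLS corrects for that difference. The listed mixed model gives each arm its own baseline mean and so carries the imbalance into the change. A non-zero relation between change and baseline is plausible, because the HbA1c test that confirms eligibility within 5.7% to 6.4% also serves as the baseline value, which invites regression to the mean. The size of that relation is not given in the documents.

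**Working it through.** **The plan's own figures.** The Sample Size section gives these inputs: "using an α of 0.017 to adjust for three main comparisons"; "Assuming a 0.4% standard deviation for 12-month HbA1c change in each arm"; "a mean 12-month absolute HbA1c decrease of 0.2% in both the Financial Incentives Arm and the Tailored Messages Arm"; "a mean 12-month absolute HbA1c decrease of 0.4" percentage points in the Combo Arm; and "85 subjects per arm will provide 99% power to detect the difference" for Combo versus control. A two-sided test is assumed.

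- SE of a difference in mean change = 0.4 × √(2/85) = 0.0614.
- Difference 0.2: 0.2/0.0614 = 3.26. Less the critical value 2.387 this is 0.87, so power is 80.9% (80.1% by noncentral t). The plan states 80%.
- Difference 0.4: power is above 99.9%. The plan states 99%.
- 85/0.9 rounds up to 95 per arm, or 380 in total, as stated.

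These figures reproduce. They rest on the unadjusted SD of change.

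**What the listed mixed model estimates.** With complete data and time as a category, the month-12 time-by-arm term equals the difference in mean 12-month change. In simulated complete data sets the two agreed to within 5e-13. The same holds for linear time, because month 6 has zero weight in a slope over 0, 6 and 12 months.

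**Size of the gap.** Let s0 be the baseline SD and k the slope of change on baseline. Ignoring strata, OLS minus the unadjusted contrast is about −k × (difference in baseline means), so its SD is about |k| × s0 × √(2/85). Assume a uniform baseline over 5.7% to 6.4%: s0 = 0.7/√12 = 0.202, and s0 × √(2/85) = 0.202 × 0.1534 = 0.031.

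The table sets this formula beside 3,000 simulated trials per slope (85 per arm, change SD 0.4, true difference 0.2, alpha 0.017, no strata effect). Disagreement is for one Combo versus single-component comparison.

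| k (assumed) | Gap SD, formula | Gap SD, simulated | Disagree on significance |
|---|---|---|---|
| −0.2 | 0.006 | 0.008 | 2.0% |
| −0.4 | 0.012 | 0.013 | 5.1% |
| −0.6 | 0.019 | 0.019 | 7.4% |

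Allowing the strata to explain up to 3% of the variance, the range over the settings tried is roughly 2% to 9%. With no true effect, disagreement was 0.5% to 0.9%. At a difference of 0.4 it was 0.0%.

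**Precision.** The baseline-adjusted residual variance is 0.16 − k²s0². For k = −0.2, −0.4 and −0.6 the residual SD is 0.398, 0.392 and 0.381. The unadjusted SE is therefore larger by 0.4/0.398, 0.4/0.392 and 0.4/0.381, or about 0.5%, 2% and 5%. Power for the 0.2 difference is about 81%, 83% and 85% adjusted, against 81% unadjusted.

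**Which terms matter.** Adding strata as main effects to the listed model moved the complete-data contrast by less than 1e-12 and left the mean SE at 0.0583, because they cancel from a within-participant contrast. They matter only when interacted with time, or when follow-up values alone are the responses.

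**Does alignment work?** In 40 complete data sets (k = −0.4, 6-to-12-month residual correlation 0.6, both assumed), the gap from OLS had SD 0.016 for the listed model. It was 0.002 for a model with 6- and 12-month responses, baseline by time, and strata main effects; the largest gaps were 0.038 and 0.006. With strata also interacted with time, every visit has the same regressors and the month-12 contrast equals OLS exactly when data are complete. Any remaining gap then comes from the longitudinal handling of incomplete data.

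**The case against.** The strongest reply is that this is a secondary analysis and the effect is small. H1a and H1b are tested by the adjusted OLS model. The sample size rests on the unadjusted change SD, so the unadjusted contrast keeps its planned 80% power. Even the gap SD of 0.019 is under 10% of the 0.2 effect and under a third of the 0.061 SE. The plan also promises to examine any difference, and a look at baseline means would expose an imbalance. All of that stands, and it limits the point to clarity of the check.

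Four stronger readings are tempting but are not supported:

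- *The two models estimate different contrasts.* Under randomisation both target the same mean difference in 12-month change.
- *Leaving out the strata inflates the mixed model's SE.* Strata main effects cancel in the listed model with complete data. The SE that a random-intercept model reports may even be too small: 0.0577 on average against an empirical SD of 0.067 in one rough scenario of 44 data sets. That is a matter of covariance structure, separate from this point.
- *The mixed model drops covariates that predict dropout.* The general rule in the opening paragraph of Analysis Plans is not confined to OLS and can be read as covering this model. Aim 1 simply does not repeat it.
- *A disagreement would say nothing about robustness.* With gaps this small, a large divergence would still be informative.

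**Conclusion.** The point holds as a modest defect in how the consistency check is specified. The listed mixed model yields an unadjusted change contrast, while OLS yields one adjusted for baseline and strata. Chance imbalance can separate them by an SD of about 0.01 to 0.02 percentage points of HbA1c, with roughly 2% to 9% disagreement on significance when the true difference is 0.2, and almost none at 0 or 0.4.

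These sizes rest on assumptions that the documents do not supply: a two-sided test, a uniform baseline over the eligible range, slopes of change on baseline from −0.2 to −0.6, and strata explaining 0% to 3% of variance. If change is unrelated to baseline and the strata have no effect, the problem all but disappears. The primary analysis and its power are not in question.

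**What to change.** In the alternate model, use the 6- and 12-month values as responses. Include as fixed effects arm by time, baseline value by time, and income and motivation strata by time. An equally standard alternative keeps baseline as a response with one common mean across arms, plus strata by time. State that the missingness-predictor rule applies to this model too, and name the month-12 arm contrast as the quantity compared with OLS. Do the same for weight.

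The cost is a sentence or two in the analysis plan and a re-run on data already collected. With follow-up values as responses, participants who have neither follow-up value leave the model, but they carry no information on change. Aim 4 under Specific Aims shows that primary and secondary outcomes had already been analysed when that aim was added. The aligned model should therefore be labelled post hoc and reported beside the listed model, not in its place.

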Consent. If determined to be preliminarily eligible from the screening questions, the potential participant is then asked to read and sign the consent form electronically, in the W2H platform. Participants will be encouraged at the start of the consent to call or email study staff if they have any questions or concerns. W2H will take them through an automated online informed consent. The consent document will be divided into sections and potential participants will have to click a button to advance through each section. This is to help ensure that participants read the consent form thoroughly by breaking down the form into manageable blocks of text. At five points in the consent document, the potential participant will be asked a question to assess the participant's understanding and to drive home key points in the consent. If answered correctly, the participant will be affirmed of their correct response; if answered incorrectly, participant needs to try again until the correct answer is selected. On the final consent screen, potential participants will choose to click one of two options: one stating that they agree to participate in the study, and the other that they do not wish to participate. The participant who agrees to participate is then to sign in a box using their mouse. In the back end of W2H, a time and date stamp indicates when the signature was submitted. The participant will have the opportunity to download the consent for their records after signing the consent and at any time they are enrolled in the study. Participants will be provided with details regarding how to contact the research team via email or phone at any time if they subsequently wish to withdraw from the study. This contact information will remain easily accessible via the participants' individual W2H dashboard throughout the study.

Final screening: A1c test. Once the consent form is signed, staff will receive a prompt to place an order in the patient's Michigan Medicine MiChart record for an A1c test. Once staff place the order, they indicate this in W2H, and an email and text are automatically sent to the participant asking them to visit any MLab to give a blood sample for the A1c test, to confirm eligibility. A link to a directory of all MLabs is included in the message. To be fully eligible for the study, patients must have an HbA1c of 5.7% to 6.4%, inclusive.

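### The alternate mixed model's random-intercept covariance does not fit the plan's own HbA1c figures, so it is an unreliable check on the primary OLS result

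*Combined protocol and SAP*

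**What the plan says.** The primary test is a single-response model: "To test H1a and H1b, we will use an OLS regression model with 12-month change in HbA1c as the response variable". It adjusts for the stratification factors, baseline HbA1c and any baseline measures that predict missing 12-month data.

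The repeated-measures model has a supporting role: "In alternate analyses, we will fit separate mixed-effects models for the primary and secondary outcomes", "using baseline, 6, and 12-month data as response variables". Its predictors are time, arm, and "interactions between time and study arm indicators as predictors and participants as random intercepts". The plan mentions no random slope, residual covariance structure or robust standard error, and does not say whether time is categorical or linear. The stratification factors are not among the predictors listed for this model.

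The authors "anticipate these longitudinal data models will confirm findings from our primary analytic approach to testing H1a and H1b", and undertake to look into any discrepancy. The opening paragraph of Analysis Plans adds: "We will assess for consistency in the results between the two analytic approaches". It applies α = 0.017 to all outcome analyses, and carries both models into the multiple-imputation analysis if more than 10% of 12-month data are missing.

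Two other places matter. Under Enrollment (final screening), "patients must have an HbA1c of 5.7% to 6.4%, inclusive", and Measures and Data Collection makes that test the baseline value. Sample Size works by "Assuming a 0.4% standard deviation for 12-month HbA1c change in each arm".

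**The concern.** With a participant random intercept and independent residuals of constant variance, all visits share one variance and every pair of visits shares one correlation (compound symmetry). The model then estimates a single variance for any between-visit difference and uses it for the 12-month change, whatever the actual variance of that change.

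A baseline held to a 0.7-point window by eligibility, beside a change SD of 0.4%, makes a common variance hard to believe. The plan also expects intervention effects to build gradually, and in that setting individual trajectories may spread apart and adjacent visits may correlate more than distant ones.

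At stake is the value of the consistency check. If the mixed model's standard error is too small, its agreement with a positive OLS result is weak support. A disagreement in either direction may reflect only the covariance assumption.

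**Working it through.** **1. The plan's own figures.** With 85 per arm, SD 0.4 and two-sided α = 0.017, power is above 0.999 for a difference of 0.4 (stated 99%) and 0.80–0.81 for 0.2 (stated 80%). 85/0.9 rounds up to 95 per arm, and 4 × 95 = 380. These reproduce. The plan gives no standard error or error rate for the mixed model, and no baseline SD, 6-month SD or between-visit correlation. Those are assumed below.

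**2. Is equal variance tenable?** A uniform spread over the window gives a baseline SD of 0.7/√12 = 0.20, or 0.8/√12 = 0.23 allowing for rounding (5.65–6.45). Clustering gives less; I use 0.15–0.23. If all visits had variance s², the variance of change would be 2s²(1 − ρ). Setting this to 0.4² = 0.16:

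- s = 0.23: ρ = 1 − 0.16/0.1058 = −0.51
- s = 0.20: ρ = 1 − 0.16/0.08 = −1
- s = 0.15: no solution

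No non-negative correlation works, so equal variance fails. (This assumes values are not piled up at both ends of the window.) Solving instead for the 12-month SD:

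SD12 = ρ·s + √(0.16 − s²(1 − ρ²))

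For s = 0.15–0.23 and ρ = 0.2–0.5, the 12-month variance is 2.7 to 9.1 times the baseline variance.

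**3. Effect on the standard error.** Let V60, V126 and V120 be the variances of the 0–6, 6–12 and 0–12 month differences. With complete data and categorical time, the random-intercept model replaces V120 by their mean:

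r = modelled SE / true SE = √[((V60 + V126 + V120)/3) / V120]

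type I error = 2[1 − Φ(2.387 r)], where 2.387 is the two-sided 0.017 critical value.

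**4. Worked example.** Take s = 0.20, corr(0,12) = 0.3, corr(6,12) = 0.7. Then SD12 = 0.06 + √(0.16 − 0.0364) = 0.412.

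- *6-month SD equal to the 12-month SD, corr(0,6) = corr(0,12).* V60 = 0.160; V126 = 2 × 0.1694 × 0.3 = 0.102; mean = 0.141; r = 0.937; type I error 0.025.
- *Gradual spread: 6-month SD 90% of the 12-month SD, corr(0,6) higher by 0.1.* V60 = 0.118; V126 = 0.093; mean = 0.124; r = 0.879; type I error 0.036.

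**5. Whole range.** Change SD 0.4 (plan); baseline SD 0.15–0.23, corr(0,12) 0.2–0.5, corr(6,12) 0.6–0.8 (assumed):

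| 6-month assumption | r | Type I error (nominal 0.017) |
|---|---|---|
| Same SD and baseline correlation as 12 months | 0.89–1.01 | 0.016–0.034 |
| SD 90% of 12-month, corr(0,6) higher by 0.1 | 0.83–0.94 | 0.024–0.047 |

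**6. Outside that range.**

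| Process (V120 = 0.16) | r | Type I error |
|---|---|---|
| Three equal difference variances | 1.00 | 0.017 |
| Equal 6/12-month SDs, s = 0.20, corr(0,t) 0.7, corr(6,12) 0.3 | 1.20 | 0.004 |
| Random walk (V60 = V126 = 0.08) | 0.82 | 0.051 |
| Pure linear random slopes (V60 = V126 = 0.04) | 0.71 | 0.091 |

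**7. Does the eligibility window cause the understatement?** No. Restricting baseline shrinks V60 and V120 relative to V126, which raises r. For an exchangeable process r goes from 1.000 to 1.01–1.03 (type I error 0.014–0.016). For AR(1) with correlation 0.8 it goes from 0.839 to about 0.855 (type I error 0.045 to about 0.042).

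**8. Simulation.** 6,000 null trials per process, 4 × 85, baseline truncated, change SD about 0.4, no stratification covariates:

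| Process | r | Mixed model type I | Primary OLS type I |
|---|---|---|---|
| Exchangeable plus noise | 1.03 | 0.016 | 0.017 |
| Random slope plus noise | 0.85 | 0.043 | 0.020 |
| Random walk | 0.81 | 0.056 | 0.018 |

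**The case against.** The strongest reply is that nothing decisive rests on this model. H1a and H1b are tested by OLS with one response per participant, so there is no between-visit covariance to misspecify, and the simulated OLS error rate stayed near nominal. That stands: no primary error rate is in question.

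Three stronger readings are tempting, and the documents support none of them.

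- *The eligibility window makes the standard error too small.* The window shows that equal variance fails, but by itself it pushes the standard error slightly upward (step 7). Understatement comes from growing variance or fading correlation.
- *The false-positive rate is about double.* Doubling needs r = 0.888, that is, V60 and V126 averaging 68% of V120. The plan gives no correlations that would establish this. With equal 6- and 12-month SDs, the error turns conservative once corr(6,12) falls below 1 − 0.16/(2·SD12²), which is about 0.44–0.62 over the assumed range.
- *The same figures apply to weight.* The model form is the same, but weight has only a BMI floor at entry and the plan gives no SD for it, so its size cannot be computed.

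It is also fair to say that the plan already promises to examine differences between the models, and that its general rule on predictors of missingness may cover part of the covariate gap. Leaving out the stratification factors would usually cost precision rather than make standard errors too small. These points soften the concern. They do not repair the check, because spurious agreement would trigger no examination.

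**Conclusion.** The point holds as a low-severity one. The planned mixed model imposes a covariance structure that the plan's own HbA1c figures contradict, given a baseline not concentrated at both ends of its window and a non-negative correlation with 12 months. Its standard error for 12-month change may be too small or too large. Gradual change makes too small the more plausible direction: type I error about 0.016–0.047 at nominal 0.017 under the assumptions in step 5, and from 0.004 to 0.091 across the other structures tried, including no inflation. All of this assumes complete data, categorical time and a two-sided test. A baseline retest after a delay of three months or more is not explicitly required to fall in range, so the restriction may be slightly incomplete.

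A reader might infer that the trial's main conclusion carries an inflated error rate. It does not. The consequence is that agreement or disagreement between the two models says less than the plan supposes.

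**What to change.** Fit the repeated-measures model with time as categorical and an unstructured covariance for the three visits. Include the two stratification factors and any baseline covariates added to the OLS model, so that the two analyses differ as little as possible. Then the comparison is sound whatever the correlations are.

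The cost is small: an unstructured 3 × 3 covariance has six parameters where the random-intercept model has two, which 380 participants support easily, and no new data are needed. Specific Aims (Aim 4) says that primary and secondary outcomes had been analysed before that aim was added. The re-fit should therefore be labelled post hoc and shown beside the model as planned, not substituted for it.
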